7.3.2. Accountability

Accountability for the IMP will be made by determining the number of Study Product vials dispensed to the patient at Day1/Baseline/V2 and at Week 2/V3 and the number of unused study medication vials returned at Week 2/V3, Week 4/V4 (EOT) Week 8/Follow-up (EOS)/V5. Accountability will be evaluated according to the following formula:

$$\text{Accountability} = 100 * \frac{(\text{number of vials dispensed}) - (\text{number of unused vials returned})}{\text{total number of vials dispensed}}$$

Below calculations will be done for treatment period and follow-up period separately to assess the accountability for IMP.

Number of vials dispensed refers to the total dispensed vials of Study Product as per the protocol up to the last date of specific study product administration. The number of vials of Study Product in each kit dispensed is **C** per protocol. Thus, the total number of vials dispensed would be calculated by number of kits dispensed multiplied by **C**.

Number of unused vials returned refers to the total unused vials of Study Product returned, over the duration for which the patient is on the treatment period.

Patient level listings of all study products administered along with reasons not dispensed study products will be provided.

The SAF, where treatment assignment is according to the actual treatment received, will be used for all summaries and listings of exposure and compliance to the study treatment. Accountability will be listed based on the SAF only.

8. Efficacy Analysis

Unless otherwise specified, all efficacy analyses with statistical hypothesis testing performed and descriptive analyses will be analyzed for the study eye only. Assessments collected for the fellow eye will be presented in listings only.

Unless otherwise specified, descriptive statistics will be used to summarize efficacy assessments for study eye at each scheduled visit. Change from baseline values for quantitative variables and shift from baseline for qualitative variables will be summarized for all available post-baseline visits by means of descriptive statistics.

CCI

All collected assessments will be presented in by-patient listings by treatment arm and ordered by site.

8.1. Primary Efficacy Endpoint

The primary endpoint is the mean change from baseline at Week 8 in symptoms of dry eye assessed by SANDE Global Score.

SANDE questionnaire includes two VAS-based questions that assess:

- DED symptom frequency (from 0 to 100)
- DED symptom severity (from 0 to 100)

compiled by the patients.

The global SANDE score (from 0 to 100) is calculated by multiplying the frequency score by the severity score and obtaining the square root. Results will be rounded to integer.

8.1.1. Primary Analysis

The overall null hypothesis H_0 is that the change from baseline in the SANDE Global Score for both of the two concentrations of rhNGF ophthalmic solution (μ_{DOSE5} and μ_{DOSE10}) are greater or equal (worse and no improvement, respectively) than the vehicle one ($\mu_{VEHICLE}$):

$$H_0 = \mu_{DOSE5} \geq \mu_{VEHICLE} \text{ and } \mu_{DOSE10} \geq \mu_{VEHICLE}$$

$$H_1 = \mu_{DOSE5} < \mu_{VEHICLE} \text{ or } \mu_{DOSE10} < \mu_{VEHICLE}$$

where μ denotes the mean change from baseline at week 8 in SANDE global score. For SANDE global Score, lower score is better.

Considering the multiple comparisons (rhNGF 5 mcg/mL versus vehicle, and rhNGF 10 mcg/mL versus vehicle) to claim overall superiority, a Bonferroni multiplicity correction of type I error will be applied on multiple comparisons. Each comparison will be consequently tested at one-sided alpha = 0.0125, in order to preserve the overall one-sided alpha of 0.025. The overall null hypothesis H_0 will be rejected if the associated primary analysis one-sided p-value will be lower than 0.0125 for one of two comparisons or both comparisons.

The primary analysis will be performed via Mixed-effects Model for Repeated Measures (MMRM) in the FAS according to the planned treatment. The analyses will include the change from baseline in SANDE global score as the dependent variable; the fixed effects of treatment (3 levels: rhNGF 5 mcg/mL, rhNGF 10 mcg/mL, and vehicle), visit (2 levels: Week 4, Week 8), baseline value, and treatment by visit interaction. An “unstructured” covariance matrix will be used. If the model fails to converge by using unstructured covariance matrix, compound symmetry matrix will be used instead. Each treatment group (IMP1 and IMP2) will be compared with the vehicle group at Week 8 using the difference in least square means (LS means) (i.e. difference between each concentration group and vehicle in mean change from baseline). The model can be summarized as follows:

$$\text{change from baseline} = \beta_0 + \beta_1 \text{treatment} + \beta_2 \text{base} + \beta_3 \text{visit} + \beta_4 \text{treatment} * \text{visit} + \varepsilon$$

where $\varepsilon \sim N(0, R)$ and R is the “unstructured” covariance matrix with blocks defined by the patients.

Based on this modeling, LS Mean, SE, and two-sided 95% CI at Week 4 and Week 8 will be provided for each treatment arm (rhNGF \square mcg/mL, rhNGF \square mcg/mL, and vehicle); difference in LS means, two-sided 95% CI, and corresponding one-sided p-value will be provided for each comparison at each timepoint. P-values for the comparisons at Week 8 will be used to declare the superiority of at least one of the \square over vehicle.

LS means change from baseline and corresponding 95% CI at Week 8 will be plotted in a forest plot by treatment arm for all main and sensitivity analysis.

Descriptive statistics for SANDE Global Score at each visit will be presented based on observed data and data after applying hypothetical strategy.

Primary Estimand:

Missing data that may be obtained notwithstanding the intent to apply the treatment policy strategy and after having applied the hypothetical strategy when needed (see [Section 3.3.1](#)), will be addressed by using multiple imputation (MI) based on copy-reference approach. This approach does not assume benefits for the rhNGF in case of discontinuation and limits a post-discontinuation clinical effect to that of the vehicle. Specifically, the copy-reference approach will be implemented in this way:

- Intermittent and monotone missing data for SANDE Global Score at baseline, Week 4 and Week 8 will be imputed by using the Fully Conditional Specification (FCS) method under the missing not at random (MNAR) assumption where only the subset of observations that come from the Vehicle group are used to derive the imputation model. The missing pattern is assumed to be arbitrary. The PROC MI procedure and FCS REGRESSION statement will be used with the seed of 47292748 and 50 imputed datasets. The minimum and maximum imputed values will be restrained to 0 and 100, respectively, via MIN and MAX options. In case of convergence issues, after imputation, imputed values lower than 0 or greater than 100 will be set to 0 and 100, respectively. The imputed values will be rounded to integers.
- For each imputed dataset, the change from baseline at Week 4 and Week 8 is derived.
- The change from baseline at Week 4 and Week 8 will then be used in a MMRM as described above with change from baseline as dependent variable and baseline value, treatment arm, visit, and treatment by visit interaction as independent variable. Patient will be considered as cluster variable and an “unstructured” covariance matrix will be set to model the within-patient correlation. If convergence fails, compound symmetry matrix will be used to model the within-patient correlation.
- Results obtained on each imputed dataset will be combined using Rubin’s rule to draw inference via PROC MIANALYZE procedure. A statistical significance level of 0.0125 will be used to declare the significance of the comparisons of each treatment arm vs vehicle.

[Appendix 13.3](#) includes the SAS code for the primary analysis illustrating the key elements for the analysis.

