10 STATISTICS

10.1 SAMPLE SIZE

The sample size of the study is calculated based on results from the previous study NGF0118 using the subgroup of patients with baseline SANDE Global Score > 50. Expecting a mean difference of about 11 points (with unequal standard deviations in the active and vehicle groups: observed mean changes (SD) were -28.2 (26.36) and -17.4 (20.29) for IMP and vehicle, respectively) in improvement of SANDE Global Score from baseline to Week 8 in favor of rhNGF ophthalmic (eye drop) formulation, a total sample size of 276 evaluable patients (92 per group) is needed. This will allow to achieve an overall power of 80% for demonstrating superiority of at least one concentration of rhNGF ophthalmic formulation over vehicle in the improvement of SANDE Global Score from baseline to week 8, with an overall one-sided alpha of 0.025.

The sample size calculation takes into consideration a Bonferroni correction for two comparisons (2 concentration groups versus vehicle), i.e., the alpha level has been set to 0.0125 one-sided for each comparison.

Assuming a 5% rate of patients not evaluable for primary analysis after enrollment, the total number of patients to be enrolled in the study will be about 291 (97 per group). Enrollment will be competitive.

In Dompé previous studies, a screen failure rate of about 20% has been observed (NGF0121 - PROTEGO-1). This fact implies that approximately 350 subjects will need to be screened in order to have 291 patients enrolled and at least 276 evaluable. In any case, the screen procedures should be interrupted when the expected sample size of 291 subjects has been reached.

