8.2. Secondary Efficacy Endpoints

8.2.1. Key Secondary Endpoints

If the primary analysis of primary endpoint leads to rejection of the null hypotheses, key secondary endpoints will be tested by using the Hochberg approach (Hochberg Y. 1988) to show superiority of each concentration for which superiority vs. vehicle has been proven in the primary analysis.

Hochberg approach will be achieved by the following procedure:

1. Put all p values in descending order and assign ranks to those p values according to their ranks.
2. Calculate each individual adjusted p-value using Hochberg approach.
3. Compare the adjusted p-values from Step 2 with the alpha level for the comparison vs. vehicle for which superiority has been shown for the primary endpoint.
4. All the tests corresponding to those p values ranking ahead of the p value selected in Step 3, including the test corresponding to the p value selected in Step 3, will be considered as significant. The null hypothesis will be rejected.

The Hochberg approach will be implemented by SAS PROC MULTTEST procedure and HOCHBERG option.

This hierarchical test strategy protects the family-wise false positive error rate at the overall one-sided 0.0125 level for each concentration vs. vehicle. With 92 patients evaluable per treatment group, the study would have approximately a power of 67% to test the endpoint with the smallest p-value in the worst-case scenario where the first 2 endpoints tested are not statistically significant (i.e. with an adjusted alpha level of 0.00417).

In case of not rejection of the null hypothesis for primary endpoint (or for the concentration for which the superiority is not shown), the above testing strategy for key secondary endpoints will not be performed. Instead, independently of results on primary endpoint, descriptive in nature analyses will be performed on all key secondary endpoints at each available timepoint by means of descriptive statistics.

Descriptive statistics for key secondary endpoints assessments at each visit will be presented based on observed data and data after applying hypothetical strategy.

8.2.1.1. Proportion of patients improving to Schirmer-I test without anesthesia ≥ 10 mm/5min in the Study Eye at week 4

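### The fixed 0.0125/0.0125 split never passes on a concentration's alpha once all its hypotheses are rejected: valid error control, but some power for the second concentration is lost

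*SAP*

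**What the plan says.** SAP 8.1.1 states that "a Bonferroni multiplicity correction of type I error will be applied on multiple comparisons" and splits the primary alpha equally: "Each comparison will be consequently tested at one-sided alpha = 0.0125, in order to preserve the overall one-sided alpha of 0.025". Its last step applies the same fixed threshold to the pooled result: "A statistical significance level of 0.0125 will be used to declare the significance of the comparisons of each treatment arm vs vehicle".

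SAP 8.2.1 then applies Hochberg to three key secondary endpoints, separately for each concentration that has won its own primary. It states that the strategy "protects the family-wise false positive error rate at the overall one-sided 0.0125 level for each concentration vs. vehicle". A concentration that misses 0.0125 on its primary gets only descriptive key secondary analyses, whatever the other achieves.

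Protocol 10.6.1, 10.6.2 and 10.6.4 carry the same scheme. Protocol 10.6.1 mentions preserving an overall one-sided 0.025 in connection with Hochberg. Protocol 10.6.4 and SAP 8.2.1 nevertheless fix 0.0125 per concentration, so that remark does not create a transfer rule.

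The sample size rests on this split: in Protocol 10.1, "the alpha level has been set to 0.0125 one-sided for each comparison".

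**The concern.** Each concentration has a branch of four hypotheses: its primary, then three key secondaries. If all four are rejected at 0.0125, nothing in that branch still needs its alpha. A rule that hands the 0.0125 to the other branch at that moment rejects everything the present plan rejects, and sometimes more, at the same overall level.

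This matters because Protocol 4.1 calls the trial dose-finding, and the end of Protocol 10.6.2 plans how to choose if both concentrations beat vehicle. At stake are the formal claims for the second concentration, on symptoms and then on signs.

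**Working it through.** **Inputs** (Protocol 10.1; repeated in part in SAP 4.1): mean changes −28.2 (SD 26.36) and −17.4 (SD 20.29), so a difference of 10.8; 92 evaluable per group; one-sided 0.0125 per comparison. The vehicle arm is shared and allocation is 1:1:1 (Protocol 6.4.2).

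**The plan's own figures.** The standard error is √((26.36² + 20.29²)/92) = √(1106.53/92) = 3.468, and 10.8/3.468 = 3.114.

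- Normal approximation at 0.0125: Φ(3.114 − 2.241) = 80.9%. The Welch version gives 80.2% at n = 92, and 92 is the smallest n reaching 80%.
- 276/0.95 = 290.5, hence 291.
- At 0.0125/3 = 0.00417 the Welch version gives 67.2%, so the 67% in SAP 8.2.1 reproduces by reusing the SANDE standardised effect.

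The plan's figures therefore hold, with one note. Protocol 10.1 claims "an overall power of 80% for demonstrating superiority of at least one concentration", but 80% is the power of a single comparison. If both concentrations have the assumed effect, simulated power for at least one is 93.2%.

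**If alpha is passed on.** The second concentration is then tested at 0.025, where its marginal power is 87.2% (Welch), against 80.2% at 0.0125. That difference applies only in trials where the first concentration has completed its branch.

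**Chance that both primaries succeed** (simulated; effect of 10.8 in both arms; correlation between the two comparisons 20.29²/1106.53 = 0.37 from the shared vehicle; endpoint correlations 0.1 to 0.6; key secondary power assumed):

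| Power of each key secondary at 0.0125 | Fixed split | With passing | Gain, points (about) |
|---|---|---|---|
| 10–30% | 0.69 | 0.69–0.70 | 0–1 |
| 50% | 0.69 | 0.70–0.71 | 1–2 |
| 67% | 0.69 | 0.72–0.73 | 3–4 |
| 80% | 0.69 | 0.74–0.75 | 5–6 |
| 90% | 0.69 | 0.76–0.77 | 7–8 |

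The 67% row is power at 0.0125. It is not the 67% of SAP 8.2.1, which is at 0.00417.

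**Conditional view.** Assume key secondary standardised effects equal to the primary's in each arm, and endpoint correlation 0 to 0.6. The first concentration then completes its branch in 43–60% of trials. Given that it does, power for the second primary changes as follows:

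- equal effects: from 85–86% to 91–92%;
- second effect 75% as large: from 59–61% to 69–72%;
- second effect half as large: from 28–30% to 39–41%.

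**Family-wise error.**

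1. If both branches contain a true null, alpha can pass only after a branch is rejected in full, including its true null. The first false rejection must therefore occur at 0.0125 within a branch, and the total is at most 0.0125 + 0.0125 = 0.025.
2. If only one branch contains a true null, that branch is tested at no more than 0.025.

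This uses the same condition the plan already needs for Hochberg to be valid within a branch. Simulation over all 255 configurations with at least one true null gave a largest error of 0.026 to 0.027, consistent with 0.025 plus simulation noise.

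**The case against.** **The plan is valid and its objective loses nothing.** This stands. A reader might infer that the split leaves type I error uncontrolled or the trial underpowered. The documents do not support either: the sample size is computed at 0.0125 per comparison, the primary objective needs only one concentration, and power for that is 93.2% with or without passing.

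**Passing is not free.** This also stands. A reader might infer that the present rule buys no error control. SAP 8.2.1 states a per-concentration level of 0.0125, and that protection is given up. With the first concentration truly effective and the second null, simulated error on the second primary rises from 0.0126 to 0.025.

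**The gain may be close to nil.** This stands as a limit. All three key secondaries must reach 0.0125. SAP 8.2.1.1 derives the Schirmer responder as a change of at least 10 mm; with entry values above 2 mm (Protocol 5.1) that needs a week 4 value above 12 mm. If that endpoint alone had 10% power and the other two 80%, the chance of both primaries succeeding would rise only from 68.6% to about 69.4%. If all key secondary effects were half the primary's, the second primary would gain about 0.2 points.

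**The harm is softened.** A concentration missing 0.0125 still gets its estimate, 95% CI, p-value and descriptive key secondary results, and the choice between concentrations uses more than significance.

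**The scheme was revised at the FDA's request** (Protocol section 13), so another rule is more than an editorial change. That is a cost, not a reason the rule would be invalid.

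Plain Holm on the primaries would gain more on the second primary (85.6%), but it would release the first concentration's alpha before its key secondaries are tested. Waiting for the whole branch avoids that conflict.

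**Conclusion.** The point holds as an optional but inexpensive gain in efficiency. The fixed split is correct and drops 0.0125 that could still be used. Passing it on after a complete branch keeps every rejection the present plan makes and holds overall family-wise error at or below 0.025. It raises the chance that both primaries succeed by anything from about 0 to 8 points. It would be tempting to quote the 7-point marginal difference (87.2% against 80.2%) as the gain. That is not the average gain, because it applies only when the first concentration has met all four endpoints.

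The range rests on both concentrations having the 10.8-point effect and on key secondary powers and correlations that neither document gives.

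**What to change.** Before unmasking, add to SAP 8.2.1: *If the primary and all three key secondary null hypotheses are rejected for one concentration at one-sided 0.0125, the primary and key secondary hypotheses of the other concentration are tested by the same procedure at one-sided 0.025.*

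That sentence alone would contradict text left in place, so also:

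- in SAP 8.1.1, change both statements of the fixed 0.0125 (the Bonferroni paragraph and the pooling step) to the level at which that concentration was tested;
- in SAP 8.2.1, change the stated 0.0125 family-wise level in the same way;
- in SAP 8.1.2, tie the tipping-point threshold to that level. Otherwise a concentration that wins with p between 0.0125 and 0.025 is past its tipping point at Δ = 0;
- list the rule in SAP section 11 as a change from Protocol 10.6. The SAP introduction makes the SAP govern where the two differ on planned analyses.

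The cost is SAP wording and programming, with no patients or data. The price in error control is that the second concentration's own error can reach 0.025. The multiplicity scheme, already revised at the regulator's request, would also gain one more rule. If the sponsor prefers to keep 0.0125 per concentration, one sentence giving that reason would settle the point. The rule cannot be added once treatment is unmasked.

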1 PROTOCOL SUMMARY

1.1 SYNOPSIS

Information	Description
Study Number	NGF0123
Title of Study (Study Name)	A 4-Week, Phase II, Multicenter, Randomized, Double-Masked, Vehicle-Controlled, Parallel Group Study With 4 Weeks of Follow-Up to Evaluate Safety and Efficacy of a new formulation of Recombinant Human Nerve Growth Factor (rhNGF) Eye Drop Solution at two different Concentrations in patients with Dry Eye Disease (REDUCO study)
IND/EudraCT No.	115892/ EUCT# 2023-507561-26-00
Centers (Country/Region)	10 to 15 sites in total (USA and Italy) Please refer to the list of approved centers in Trial Master File
Development Phase	Phase II
Background Information	
Nerve growth factor (NGF) is a polypeptide essential for the survival and growth of sympathetic and sensory neurons, and for differentiation of neurons in the central nervous system (Levi-Montalcini, R. 1987). NGF and its receptors TrkA and p75 are expressed in the anterior segment of the eye (iris, ciliary body, lens, cornea, and conjunctiva), and NGF is released in the aqueous humor. Studies suggest that NGF affects all tissues of the anterior segment, hence playing a crucial role in the pathophysiology of several diseases of the anterior segment of the eye (Lambiase, A. et al. 2011).
 
Dry eye disease (DED) is a multifactorial disease of the ocular surface, characterized by impairment of quantity of tears and/or quality of the tear film. It is also accompanied by tear film hyperosmolality, ocular discomfort symptoms, ocular surface inflammation and damage, and neurosensory abnormalities (Craig, J.P. et al. 2017). Until now, treatment has been limited to the use of artificial tears or varenicline to temporarily improve lubrication of the ocular surface, or to the use of topical steroids, cyclosporine A or lifitegrast to decrease the inflammatory reaction.
 
Experimental and clinical evidence suggests that NGF may affect all the pathogenic mechanisms of dry eye, potentially restoring ocular surface homeostasis (Lambiase, A. et al. 2012). Specifically, NGF has been shown to stimulate tear film production, promote corneal epithelial healing, and stimulate conjunctival epithelial differentiation and mucin secretion (Coassin, et al. 2005; Lee, et al. 2006; Bonini, et al. 2000; Rios, et al. 2007).
 
OXERVATE® is a 0.002% ( mcg/mL) recombinant human nerve

Information	Description

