10.6.4 Secondary and Exploratory Analysis

If the primary analysis of primary endpoint leads to rejection of the null hypotheses, key secondary endpoints will be tested by using the Hochberg approach (Hochberg Y. 1988) to show superiority of each concentration for which superiority vs. vehicle has been proven in the primary analysis.

This test strategy protects the family-wise false positive error rate at the overall one-sided 0.0125 level for each concentration vs. vehicle. With 92 subjects evaluable per treatment group, the study would have approximately a power of 67% to test the endpoint with the smallest p-value in the worst-case scenario where the first 2 endpoints tested are not statistically significant (i.e., with an adjusted alpha level of 0.00417).

Key secondary endpoints will be analyzed with the same strategy described for the primary endpoint for the multiple imputation. Multiple imputation for Schirmer-I test will be done once for both continuous and dichotomous endpoints that will be derived (i.e., change from baseline and improvement ≥ 10 mm/5min will be derived after the imputation of the continuous values). An ANCOVA model with treatment and baseline value will be used instead of the MMRM for the two continuous endpoints since these are evaluated at Week 4. For the same reason, only baseline and week 4 data will be used in the multiple imputation described in § 10.6.2. The binary key secondary endpoint will be analyzed in analogy with the other key secondary endpoints, but a logistic model will be used instead of an ANCOVA model with baseline value and treatment as covariates.

In case of not rejection of the null hypothesis (or for the concentration for which the superiority is not shown), the above testing strategy will not be performed. Instead, independently of results on primary endpoint, descriptive in nature analyses will be performed on all key secondary and secondary endpoints at each available timepoint by means of descriptive statistics and by appropriate parametric or non-parametric tests depending on the distribution of each parameter. Change from baseline values and shift tables versus baseline may be summarized for all available post-baseline visits.

Further details will be provided in the SAP.

Details on the statistical methods that will be used for the additional objective (i.e., the validation of the Italian version of the CCI [REDACTED]) will be provided in the SAP.

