4.2. Randomization, Stratification, and Masking

Interaction Response Technology (IRT) will be used to randomize the patients in a 1:1:1 ratio to each of the three treatment arms.

Eligible patients will be randomized in a 1:1:1 ratio to rhNGF **C** mcg/mL **CCl** (about 97 patients), rhNGF **C** mcg/mL **CCl** (about 97 patients) or vehicle ophthalmic solution **CC** (about 97 patients). Patients in the vehicle arm will be randomly assigned 1:1 to two different vehicle filling volumes to preserve masking. Nevertheless, all the patients randomized to the vehicle arm will be analyzed as a single treatment arm.

Each randomized patient will be allocated with a randomization number, according to the stratified randomization list. Dropouts after randomization will not be replaced.

Randomization will be stratified by site to ensure balanced assignment across treatment groups within each site. The stratified permuted block randomization list will be generated with a computer procedure by an independent statistician not involved in the conduct of the study.

This is a double-masked study. Appearance, including packaging and labeling, of the study products (IMP or vehicle) will not allow recognition of the actual treatment. Masked information on the identity of the assigned study products will be provided for each patient.

Unmasking can only occur in case of emergency, when knowledge of the treatment identity is essential for treating the patient. If the treatment code needs to be broken in the interest of patient safety for a medical emergency, the Investigator is allowed to break the treatment code for the specific patient, even before informing the Sponsor.

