Missing data will be imputed by using a multiple imputation with copy-reference approach (see [Section 8.1.1](#)). For each imputed dataset, the change from baseline at Week 4 is derived. Patients with change from baseline at Week 4 ≥ 10 mm/5min will be considered as having improvement while patients with change from baseline at Week 4 < 10 mm/5mins will be considered as not having improvement. 95% CI on proportion of patients having improvement will be implemented by using Clopper Pearson method.

The derived binary variable described in the previous step will then be used in a logistic model as dependent variable; treatment (3 levels: rhNGF \blacksquare mcg/mL, rhNGF \blacksquare mcg/mL, and vehicle) and baseline Schirmer-I scores in the Study Eye as covariates.

Based on this modeling, the estimated proportions and corresponding two-sided 95% CI will be provided for each treatment arm; the estimated mean proportion differences, two-sided 95% CI, and corresponding one-sided p-value will be provided for each IMP group versus vehicle at Week 4.

8.2.1.2. Mean change from baseline in Schirmer-I score without anesthesia in the Study Eye at Week 4

The MI procedure described in [Section 8.2.1.1](#) will be applied to impute missing Schirmer-I scores at Week 4. Change from baseline at Week 4 will be fitted in the ANCOVA model with change from baseline at Week 4 as dependent variable, treatment (3 levels: rhNGF \blacksquare mcg/mL, rhNGF \blacksquare mcg/mL, and vehicle) and baseline Schirmer-I scores in the Study Eye as covariates.

Based on this modeling, a point estimate (the adjusted estimated treatment effect), associate SE, two-sided 95% CI, and corresponding one-sided p-value will be provided for each treatment group; a point estimate (the adjusted estimated treatment difference), associate SE, two-sided 95% CI, and corresponding one-sided p-value will be provided for each least squares (LS) mean treatment difference versus placebo at Week 4.

8.2.1.3. Mean change from baseline in total corneal fluorescein staining (NEI scale) in the Study Eye as assessed by the investigator at week 4

Corneal fluorescein staining has 5 zones and each zone has a score range of 0-3. The total score is determined by simply adding up the scores of the 5 individual zones. The range of total corneal fluorescein staining in NEI scale is 0-15. If any of the 5 individual zones has a missing score, the total score would be missing.

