13.3. SAS Code for Primary Analysis

Step 1: Multiple Imputation

```
PROC SORT data=efficacy;  
  by USUBJID;  
RUN;
```

```
PROC MI data=efficacy nimpute=50 out=mi_data min=0 max=100 seed= 47292748; *score range: 0-100;  
  class TRTPN;  
  var V2 V4 V5; *V2=baseline, V4=Week 4, V5=Week 8;  
  FCS regression;  
  mnar model(V2 V4 V5/ modelobs=(TRTPN='3')); *Vehicle group has TRTPN=3;  
RUN;
```

Data will be transformed to short format by AVISITN before applying multiple imputation.
The MI method will be used for both primary and secondary analyses after applying appropriate ICE handling strategies.

Step 2: MMRM Model

```
PROC MIXED data= mi_data_long;  
  by _imputation;  
  class TRTPN AVISITN USUBJID;  
  model CHG=BASE TRTPN AVISITN TRTPN*AVISITN / DDFM=KR CL;  
  repeated AVISITN/subject=USUBJID type=UN;  
  lsmeans TRTPN*AVISITN/diff cl;  
  ods output lsmeans=lsM diffs=diffM;  
RUN;
```

Data will be transformed back to long format by combining visits before applying MMRM model.
If model fails to converge, the “type=UN” will be replaced by “type=CS”.
This model is the essential model for primary endpoint. Appropriate adjustments may be made based on modified Estimand strategies and sensitivity analyses.

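### Site stratifies the randomisation but is left out of the primary and key secondary models, so the tests will be conservative if sites still differ after baseline adjustment

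*SAP*

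**What the plan says.** SAP 4.2 states: "Randomization will be stratified by site to ensure balanced assignment across treatment groups within each site". Protocol 6.4.2 has the same rule, using permuted blocks. The Protocol synopsis (1.1) plans 10 to 15 sites in the US and Italy.

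The models are as follows:

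- **Primary MMRM.** SAP 8.1.1 lists treatment, "visit (2 levels: Week 4, Week 8), baseline value, and treatment by visit interaction". The model equations there and in Protocol 10.6.2 match this list. The code in SAP 13.3 reads "model CHG=BASE TRTPN AVISITN TRTPN*AVISITN / DDFM=KR CL"; its CLASS statement holds only treatment, visit and subject, and it has no RANDOM statement.
- **Two continuous key secondaries** (Schirmer-I and corneal staining, week 4). Protocol 10.6.4 says: "An ANCOVA model with treatment and baseline value will be used instead of the MMRM for the two continuous endpoints".
- **Binary key secondary** (Schirmer-I response, week 4). Protocol 10.6.4 says: "a logistic model will be used instead of an ANCOVA model with baseline value and treatment as covariates". SAP 8.2.1.1 agrees, naming treatment and "baseline Schirmer-I scores in the Study Eye as covariates", and reports the result as a difference in proportions.

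No sensitivity or supportive analysis in SAP 8.1.2 or 8.1.3 adds site. Elsewhere in the SAP site mainly orders listings, and region (EU, US) is a subgroup variable in 8.4. No reason for the omission is given. Part of the general text in SAP section 8 is blacked out, and nothing here rests on it; the equations and the code are legible.

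**The concern.** Blocking within site balances the arms inside each site, so a difference in average outcome between sites largely cancels out of the treatment comparison. A model without site does not take account of that. It leaves the between-site variation in the residual, and the standard error it reports is larger than the true sampling error of the estimate. Confidence intervals are then too wide, and each one-sided test at 0.0125 rejects less often than it should under the null.

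What is at stake is efficiency. The design pays for within-site balance, and the analysis does not collect the benefit. Whether there is any benefit to collect depends on how much sites differ once baseline is in the model.

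**Working it through.** **Inputs.** Protocol 10.1 and SAP 4.1 give mean changes (SD) of -28.2 (26.36) on active and -17.4 (20.29) on vehicle, so the difference is 10.8, with 92 evaluable patients per group. Protocol 10.1 sets one-sided alpha at 0.0125 per comparison, with critical value 2.2414. The between-site share of residual variance, R, is not in the documents and is assumed.

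**The plan's own figure.** The root-mean-square SD is sqrt((26.36² + 20.29²)/2) = 23.52. For 80% power the normal formula gives 91 per group; the t-test and Welch versions give 92. Then 92/0.95 = 96.8, rounded up to 97, and 3 × 97 = 291. The planned size is reproduced from total SDs, with no credit for site adjustment.

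**Effect of leaving out site.**

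- Reported SE without site: SE0 = sqrt((694.85 + 411.68)/92) = 3.468.
- True SE under stratified allocation: SE = SE0 × sqrt(1 − R).
- Actual size without site: 1 − Φ(2.2414 × SE0/SE).
- Power without site: 1 − Φ((2.2414 × SE0 − 10.8)/SE).
- Power with site: 1 − Φ(2.2414 − 10.8/SE).

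| R (assumed) | SE0/SE | Actual size without site | Power without site | Power with site | Forgone (points) |
|---|---|---|---|---|---|
| 0% | 1.000 | 0.0125 | 80.9% | 80.9% | 0 |
| 2% | 1.010 | 0.0118 | 81.1% | 81.7% | 0.6 |
| 5% | 1.026 | 0.0107 | 81.5% | 83.0% | 1.5 |
| 10% | 1.054 | 0.0091 | 82.1% | 85.1% | 3.0 |
| 15% | 1.085 | 0.0075 | 82.8% | 87.2% | 4.4 |

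**Common variance, as in the planned MMRM.** The code fits one covariance matrix to all three arms. With the same SDs and no baseline adjustment, the reported SE is sqrt(((2 × 694.85 + 411.68)/3) × 2/92) = 3.61. Even at R = 0 that gives a size of 0.0098 and power of 78.2%, a departure that has nothing to do with site. The gap with versus without site becomes 1.7 points at 5% and 3.4 at 10%, slightly more than in the table.

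**Simulation check, continuous outcome.** This was a single-timepoint ANCOVA with 276 patients, unequal site sizes, a common SD of 23.52 and an assumed block size of 6. At R = 10%, power was 82.0% without site against 84.9% with it (10 sites), and 80.6% against 83.7% (15 sites). At R = 0, the mean SE was 3.470 without site, against 3.473 with 10 sites and 3.480 with 15 sites in the model.

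**Simulation check, logistic model.** This used 12 sites, 276 patients, no baseline covariate, an assumed vehicle log-odds of −1.4 and a treatment log-odds ratio of 0.8.

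| Site SD (logit, assumed) | SE of proportion difference, without / with site | Power on that scale | Log-odds estimate (SE), without / with site |
|---|---|---|---|
| 0 | 0.0646 / 0.0634 | 59.3% / 60.7% | 0.816 (0.343) / 0.852 (0.351) |
| 0.4 | 0.0652 / 0.0631 | 53.1% / 56.6% | 0.764 (0.338) / 0.820 (0.351) |
| 0.8 | 0.0661 / 0.0614 | 51.5% / 58.9% | 0.744 (0.334) / 0.869 (0.361) |

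The gain in this table is somewhat flattering. At site SD 0 the site-adjusted model already shows 1.4 points more power with nothing to gain. Its SE also falls below the simulated SD of the estimate (0.0631 against 0.0645 at SD 0.4; 0.0614 against 0.0634 at SD 0.8).

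**The case against.** The strongest reply is that no planned property fails. The sample size takes total SDs, so the protocol never counted on a site-adjusted analysis, and in the table power without site stays above 80% at every value of R. The error is in the safe direction. SANDE is completed by the patient, the outcome is change from baseline, and baseline is already in the model, so much of any site difference may be absorbed. Nothing in the documents shows that sites, or the US and Italy, differ. All of this stands, and it limits the point to one of efficiency.

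The absolute size and power values are also not those of the planned test. They come from a two-sample calculation with unequal variances and no baseline adjustment. That stands too: they are illustrative, and the gap between the two analyses is the usable result.

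A reader might infer that standard errors are too large in every model and on every scale. For the logistic model that is not so. On the log-odds scale the SE without site is smaller, and it is the estimate that is pulled towards zero. The statement holds for the difference in proportions, which is what the SAP reports.

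Finally, the change is more than one line of code. The imputation in SAP 13.3 uses only the three visit scores, modelled on vehicle patients, and 9 to 14 site terms can cause separation in the logistic model if responders are few. Both are fair and are taken up in the fix.

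**Conclusion.** The mismatch between randomisation and analysis is certain; its effect is conditional. If sites differ after baseline adjustment, the primary and key secondary tests are conservative and some power goes unused: for the primary comparison, about 0.6 points at a residual site share of 2%, 1.5 at 5%, 3.0 at 10% and 4.4 at 15%, and slightly more under a common variance. If sites do not differ, nothing is lost.

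A reader might go further and infer that precision has demonstrably been lost, that type I error is inflated, or that the trial falls short of its 80%. The documents support none of these. They give no between-site variance, the direction is conservative, and the loss is measured against a site-adjusted analysis rather than against the plan. The change is worth making because it costs little, but no conclusion of the trial is invalid without it.

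**What to change.** Before unmasking:

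- Add site as a fixed effect to the MMRM, the two ANCOVAs and the logistic model, in the SAP text, equation and code. Record the change in SAP section 11, since the protocol models also omit site.
- Set a masked, pre-specified rule for pooling small sites within country. The documents do not state the block size, so choose the threshold from masked enrolment counts.
- For the logistic model, name region (EU, US) as the fallback if separation occurs.
- State whether site enters the imputation model, and why.

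The cost is 9 to 14 degrees of freedom out of 276 evaluable patients, a pooling rule and some SAP wording. If sites do not differ, the simulated SE rises only from 3.470 to between 3.473 and 3.480. If the sponsor prefers to keep the models as they are, the SAP should say why and add a site-adjusted sensitivity analysis.
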